**Opt-in versus opt-out clinical trial enrollment
among patients with peripheral artery disease:
A GAME PAD substudy**

Version 2

November 09, 2020

1. Background

Research studies are hampered by low participation rates, threatening these studies' external validity, prolonging study timelines, and increasing costs.(1,2) Behavioral economics research has shown that framing retirement savings and organ donation participation as opt-out rather than opt-in increases participation in these programs while maintaining informed choice.(3) In healthcare, an opt-out approach has also been shown to increase influenza vaccination and human immunodeficiency virus screening.(4,5) More recently, a randomized controlled trial testing opt-in versus opt-out approaches to colorectal cancer screening by fecal occult blood testing showed that the opt-out approach increased participation rates nearly 3-fold.(6)

In clinical trials of home-based monitoring for patients with myocardial infarction and a behavioral intervention for patients with poorly-controlled diabetes mellitus, sub-studies have shown that an opt-out approach increased enrollment compared with an opt-in approach.(7,8) In a trial of a home-based monitoring program for patients with myocardial infarction, eligible patients were enrolled using a traditional opt-in approach.(7) These patients were sent a recruitment letter after their myocardial infarction, contacted via phone and consented for enrollment, and, after consent, sent a remote monitoring medication bottles, entered into a system configured with financial incentives, reminders, and social support. A separate cohort of patients, made ineligible for participation by their insurance type, was sent configured medication bottles along with their recruitment letters to create an opt-out frame. In the opt-in arm, 16% of patients agreed to participate in the study, compared with 38% in the opt-out arm. In a trial of a behavioral intervention for patients with poorly controlled diabetes mellitus, patients were randomized to receive a letter informing them that they had been enrolled in a clinical trial (opt-out) versus a standard recruitment letter (opt-in).(8) In the opt-in arm, 13% of patients agreed to participate compared with 38% in the opt-out arm.

Though opt-out trial participation has increased enrollment in two prior studies, it is uncertain whether it will do the same in a clinical trial intended to promote physical activity in patients with peripheral artery disease (PAD), as these patients differ from those included in the myocardial infarction and diabetes trial in several ways, and the intervention differs as well. We therefore seek to conduct a randomized substudy of the proposed GAME PAD randomized controlled trial, evaluating the effect of opt-out versus opt-in framing of clinical trial enrollment.

2. Study Objectives

The objectives of this study are the following:

1. To determine the effect of an opt-out versus an opt-in approach to enrollment in a clinical trial enrolling patients with peripheral artery disease on the proportion of patients contacted enrolled
2. To determine the effect of an opt-out versus an opt-in approach to enrollment in a clinical trial enrolling patients with peripheral artery disease on the clinical characteristics of patients who decide to enroll in the study

3. Sub-Study Design and Procedures

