3.1 General overview

The GAME PAD study is a two-arm randomized controlled trial aimed at evaluating whether a home-based walking program with automated coaching augmented with gamification and behavioral economic principles improves functional capacity in patients with PAD. The study will randomize 100 patients with PAD to a 16-week home-based walking program using goal-setting alone (attention control) or to the same home-based walking program with automated coaching augmented with gamification and behavioral economic principles. The study will be conducted using the Way to Health platform, and patients will enroll and consent for participation online, with available help from a study coordinator by telephone. This sub-study will test whether opt-in or opt-out framing of study participation upon initial contact affects the proportion of patients who ultimately enroll in the study and the demographic characteristics of enrolled patients.

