3.4.3 Data collection

Baseline characteristics of patients randomized to each framing method will be abstracted from the electronic health record and Penn Data Store, and will include age, sex, race/ethnicity, and medical comorbidities. Whether contacted patients created an account on the Way to Health website and/or ultimately consented for enrollment in the study will be captured.

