3.4.4 Outcomes

For all outcomes, we will compare patients initially presented with study participation via opt-in framing versus opt-out framing. The primary outcome will be the proportion of patients that enroll in the study. Exploratory outcomes, among patients that ultimately enrolled in the study, will include the proportion of enrolled patients that failed to complete the study, change in daily step count from baseline to the end of the GAME PAD intervention and the end of follow-up (overall and stratified by overall GAME PAD study arm – gamification intervention versus attention control), and change in patient-reported symptom scores from baseline to the end of the GAME PAD intervention and the end of follow-up (overall and stratified by overall GAME PAD study arm)

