3.4.5 Informed consent

Because the trial tests different methods of approaching patients prior to enrollment, informed consent cannot feasibly be obtained and we will request a waiver of informed consent

4. Statistical Analysis

We will compare the primary outcome and attrition rate between patients initially presented with study participation via opt-in framing versus opt-out framing using the chi-square method. Change in step count from baseline through the intervention period and follow-up will be compared using paired t tests, as will change in patient reported symptom scores from baseline through the intervention period and the end of follow up. The primary outcome will be analyzed using the intention-to-treat principle, grouping patients by framing of study participation at initial contact. Other outcomes, among patients that ultimately enrolled in the GAME PAD study, will similarly group patients by framing of study participation at initial contact.

5. Human Research Protection

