5.6.2 Potential study benefits

No benefits are expected to accrue to participants in the study. However, better understanding the effect of opt-out design on clinical trial participation has the potential to increase clinical trial

participation in the future, increasing the representativeness and reducing the cost of future clinical trials.

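### Does Objective 2 need its own outcome line and a comparison with all contacted patients before it can be answered?

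*Combined protocol and SAP*

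**What the plan says.** Section 2 sets two objectives. The first concerns the proportion enrolled. The second is the effect of framing "on the clinical characteristics of patients who decide to enroll in the study". Section 3.1 restates the aims: the sub-study tests whether framing "affects the proportion of patients who ultimately enroll in the study and the demographic characteristics of enrolled patients".

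Section 3.4.3 covers the data: "Baseline characteristics of patients randomized to each framing method will be abstracted from the electronic health record and Penn Data Store". The items are age, sex, race/ethnicity and comorbidities. The same section captures whether each contacted patient consented.

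Section 3.4.4 makes enrollment the primary outcome and continues: "Exploratory outcomes, among patients that ultimately enrolled in the study, will include the proportion of enrolled patients that failed to complete the study". Changes in step count and symptom scores follow. No baseline characteristic is listed.

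Section 4 gives chi-square tests for enrollment and attrition and t tests for step count and symptom scores. It adds: "Other outcomes, among patients that ultimately enrolled in the GAME PAD study, will similarly group patients by framing of study participation at initial contact".

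On motive, Section 1 says that low participation is a threat to "external validity, prolonging study timelines, and increasing costs". Section 5.6.2 names "increasing the representativeness and reducing the cost of future clinical trials" as something that may follow if participation rises.

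**The concern.** One of only two objectives has no matching outcome and no stated analysis. Section 2 calls the characteristics clinical and Section 3.1 calls them demographic. The comorbidities are not itemized, so the choice of variables could wait until the data are seen.

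The second worry is about the contrast. If Section 4's rule for other outcomes is applied to characteristics, the result is one table of opt-in enrollees beside opt-out enrollees. Representativeness compares enrollees with the people approached, and that table leaves them out. Reading a higher share of some group among opt-out enrollees as better representation could be right or exactly wrong, and the table would look the same either way. The baseline data on everyone randomized would settle it, but no section assigns them that use.

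**Working it through.** The plan states no sample size, power or effect size for the sub-study, so there is no figure to reproduce. The check has four steps.

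**1. Does the enrollee table answer Objective 2?** Take a binary characteristic with share c among contacted patients. In arm a, let r(a) be the overall enrollment rate and r1(a) the rate among those with the characteristic. The share among that arm's enrollees is

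c × r1(a) / r(a).

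Randomization (Section 3.4.1) makes c the same in both arms in expectation. The between-arm difference is therefore

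c × [r1(out)/r(out) − r1(in)/r(in)].

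Apart from chance, it is non-zero only if framing changes who enrolls. That is the question in Objective 2.

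**2. What would a contacted-patient column add?** Assume shares of 30% among opt-in and 45% among opt-out enrollees (illustrative; the plan gives none).

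| Contacted share (assumed) | Opt-in gap | Opt-out gap | Opt-out minus opt-in |
|---|---|---|---|
| 50% | 30 − 50 = −20 | 45 − 50 = −5 | 15 |
| 25% | 30 − 25 = +5 | 45 − 25 = +20 | 15 |

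Which arm is closer reverses at (30 + 45)/2 = 37.5%. So the column does carry information on representativeness. The last column does not move, because c cancels: the answer to Objective 2 is the same with or without it. At an opt-out enrollment rate of 38%, the 25% row also requires enrollment of 0.38 × 0.45/0.25 = 68.4% with the characteristic and 0.38 × 0.55/0.75 = 27.9% without it, which is an extreme pattern.

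**3. How precise would the answers be?** Inputs: 100 patients in the main trial (Section 3.1), 3:1 allocation (Section 3.4.1), and the earlier diabetes trial's rates of 13% and 38% (Section 1), used for illustration.

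- Contacted: 100/(0.75 × 0.13 + 0.25 × 0.38) = 100/0.1925, about 519.
- Enrollees: 519.5 × 0.75 × 0.13 = 50.6 opt-in and 519.5 × 0.25 × 0.38 = 49.4 opt-out.
- Between-arm 95% half-width: 1.96 × √(0.30 × 0.70/50.6 + 0.45 × 0.55/49.4) = 18.8 points, around a difference of 15.
- Gap half-widths, taking the contacted share as fixed: 1.96 × √(0.30 × 0.70/50.6) = 12.6 points (opt-in) and 1.96 × √(0.45 × 0.55/49.4) = 13.9 points (opt-out).

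The contacted share may be treated as fixed because Section 3.4.3 abstracts it for everyone randomized. The 5-point gaps in step 2 lie well inside these intervals. With the myocardial infarction trial's 16% and 38% the picture is much the same: 100/0.215, about 465 contacted, with 55.8 and 44.2 enrollees.

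**4. Is the contacted group a clean reference?** Section 3.3 sets no exclusions for the sub-study and refers to a separate protocol for the main trial's criteria. Enrollees must pass those criteria; contacted patients need not. A gap between the two therefore mixes willingness to enroll with eligibility, in proportions that these documents cannot separate. The between-arm contrast largely avoids this, because the same criteria apply in both arms.

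**The case for a change.** The strongest case for a change is that an objective should have a named outcome, and that a few sentences would supply it without new data. Readers will draw conclusions about representativeness whether or not the plan invites them, since Sections 1 and 5.6.2 raise the subject. An open comorbidity list leaves room for selective emphasis.

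Part of this stands. The outcome line is missing, "the demographic characteristics of enrolled patients" in Section 3.1 does not match Section 2, and the comorbidities are not named. These are gaps in detail. Section 3.4.3 names the other variables and covers both demographic and clinical kinds, and the two arms define the comparison. An analyst would produce a table of characteristics by framing among enrollees.

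The argument about representativeness does not stand as a fault. Sections 1 and 5.6.2 both reach it through higher participation, which is the primary outcome, and neither commits the sub-study to measuring it. Nor does the plan prevent such a table. If characteristics are not a listed outcome, Section 4's rule for other outcomes does not clearly confine them to enrollees, and nothing bars use of the data on all randomized patients.

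**Conclusion.** No change to the plan is needed. Following it gives a sound answer to Objective 2 as worded, because randomization makes opt-in against opt-out enrollees the matching contrast. The missing outcome line and the mixed wording are omissions of detail in a descriptive part of the analysis, and the primary comparison of enrollment is untouched. Showing contacted patients alongside is an optional extra. It leaves the between-arm difference unchanged, carries uncertainty of about 13 to 14 points per arm in the example, and would have to be read with the main trial's eligibility criteria in mind. The figures rest on assumed shares of 30% and 45%, 100 enrollees, and enrollment rates borrowed from an earlier trial. The conclusion on the contrast needs only that both arms are randomized from one contacted population and face the same main-trial criteria.

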3.1 General overview

The GAME PAD study is a two-arm randomized controlled trial aimed at evaluating whether a home-based walking program with automated coaching augmented with gamification and behavioral economic principles improves functional capacity in patients with PAD. The study will randomize 100 patients with PAD to a 16-week home-based walking program using goal-setting alone (attention control) or to the same home-based walking program with automated coaching augmented with gamification and behavioral economic principles. The study will be conducted using the Way to Health platform, and patients will enroll and consent for participation online, with available help from a study coordinator by telephone. This sub-study will test whether opt-in or opt-out framing of study participation upon initial contact affects the proportion of patients who ultimately enroll in the study and the demographic characteristics of enrolled patients.

3.2. Site

This GAME PAD substudy will enroll patients from the University of Pennsylvania Health System, which consists of five large hospitals including the Hospital of the University of Pennsylvania, Penn Presbyterian Medical Center, Pennsylvania Hospital, and Chester County Hospital.

3.3. Patient Selection Criteria

Patients are eligible to be included in the study if they are ≥ 18 years of age, have been seen in the University of Pennsylvania Health System, and have an ICD-10 code consistent with peripheral artery disease (I70.2x, I70.3x-I70.7x, I73.9) or peripheral artery disease on their problem list. There are no exclusion criteria.

Please refer to the separate protocol for inclusion and exclusion criteria for the main GAME PAD study.

3.4. Substudy procedures

3.4.1 Randomization

Eligible patients will be contacted via email to determine their interest in participation in the GAME PAD study. Patients will be randomized 3:1 to an email message framing trial participation in a standard opt-in manner versus an email message framing trial participation in an opt-out manner.

3.4.2 Study arms

Patients randomized to opt-in framing will be instructed to visit the Way to Health website to enroll in the study, or to call or email the study coordinator with questions or for assistance in enrolling. Patients randomized to opt-out framing will receive an email that frames participation in the study as part of the standard of care, and will be informed that a study coordinator will be calling them in the coming days to start enrollment in the study unless they opt out of participation.

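### Does the coordinator call announced only in the opt-out arm undermine the comparison of opt-in and opt-out enrollment?

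*Combined protocol and SAP*

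**What the plan says.** Section 3.4.1 randomizes patients 3:1 to "an email message framing trial participation in a standard opt-in manner versus an email message framing trial participation in an opt-out manner". Section 3.1 states the purpose in the same terms: "This sub-study will test whether opt-in or opt-out framing of study participation upon initial contact affects the proportion of patients who ultimately enroll". Neither passage mentions an outbound call as part of the contrast.

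Section 3.4.2, which defines the arms, goes further. Opt-in patients are directed to the website and may contact the coordinator themselves. Opt-out patients receive an email that presents the study as belonging to usual care and says that "a study coordinator will be calling them in the coming days to start enrollment in the study unless they opt out of participation".

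The first objective in section 2 uses a broader word than framing: "To determine the effect of an opt-out versus an opt-in approach to enrollment in a clinical trial". Section 3.1 also says that "patients will enroll and consent for participation online, with available help from a study coordinator by telephone", without naming an arm. Section 3.4.3 records account creation and consent. Section 4 compares enrollment by chi-square under intention to treat, grouped by the framing assigned.

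**The concern.** If the randomized contrast is two emails, an outbound call in one arm is a second intervention that acts directly on the primary outcome. A higher enrollment rate in the opt-out arm could then come from the call rather than the wording, and the analysis could not tell them apart. Nor is a call peculiar to opt-out recruitment: section 1 reports that opt-in patients in the myocardial infarction precedent were telephoned too.

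The document leaves details open. It does not say outright that opt-in patients receive no outbound call, it gives no number of attempts or time limit, and it does not list calls, opt-outs or route of enrollment among the data. At stake would be a mistaken claim about email wording, or an unexplained small difference if some announced calls were never made.

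**Working it through.** The plan states no sample size, power or significance level for the substudy, so there is no figure of its own to reproduce. The question is settled mainly by reading the sections together; the arithmetic shows how large the effects could be.

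**1. Is the call part of the randomized intervention?**
- Section 3.4.2, headed as the definition of the arms, describes the opt-out arm as email plus announced call.
- Section 2 asks about an approach to enrollment, which covers both.
- Section 1 uses the term frame in the same broad way: in the myocardial infarction precedent a separate cohort "was sent configured medication bottles along with their recruitment letters to create an opt-out frame". Shipping bottles is an operational step, as the call is here. An opt-out default needs some step that goes ahead unless the patient refuses.

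Allocation is random and patients are analyzed as assigned, so the difference in proportions estimates the effect of assignment to the whole approach. If that approach has no effect, the chi-square test keeps its nominal error rate.

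**2. Could the call alone produce a positive result?** Assume no wording effect, an opt-in rate p_in, and a call that converts a share q of opt-out patients who would not otherwise enroll. Assume also two-sided alpha 0.05, 3:1 read as opt-in to opt-out, and enough contacts for 100 enrollees (section 3.1: "The study will randomize 100 patients with PAD").

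p_out = p_in + (1 − p_in) × q; contacts N = 100 / (0.75 × p_in + 0.25 × p_out).

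For p_in = 0.16 and q = 0.10:
- p_out = 0.16 + 0.84 × 0.10 = 0.244
- N = 100 / (0.120 + 0.061) = 552, or 414 opt-in and 138 opt-out
- Pooled rate 0.181; standard error under the null √[0.181 × 0.819 × (1/414 + 1/138)] = 0.0378; under the alternative √[0.16 × 0.84/414 + 0.244 × 0.756/138] = 0.0407
- Power = Φ[(0.084 − 1.96 × 0.0378) / 0.0407] = Φ(0.24) ≈ 0.60

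| p_in | q = 5% | q = 10% | q = 15% |
|---|---|---|---|
| 16% | 0.225 | 0.596 | 0.864 |
| 13% | 0.313 | 0.748 | 0.949 |

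So the call could carry the result. These are false positives only if the call lies outside the intervention. Under sections 2 and 3.4.2 it lies inside, and they are the power to detect a real effect of the approach.

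**3. Size at the precedent rates.** Assume all 100 enrollees come from these emails.
- 13% vs 38%: 100 / (0.75 × 0.13 + 0.25 × 0.38) = 519.5 contacted (389.6 and 129.9)
- 16% vs 38%: 100 / (0.75 × 0.16 + 0.25 × 0.38) = 465.1 contacted (348.8 and 116.3)
- Opt-out patients assigned per additional enrollee: 1/0.25 = 4.0 and 1/0.22 = 4.5

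The last line is an upper bound on patients called, because those who opt out are not called and some may enroll first.

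**4. Missed calls.** If a share f of opt-out patients is never called and enrolls at the opt-in rate, the observed difference is (1 − f) × (p_out − p_in).
- f = 0.10: 0.90 × 25 = 22.5 points; 0.90 × 22 = 19.8 points
- f = 0.25: 0.75 × 25 = 18.8 points; 0.75 × 22 = 16.5 points

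This is a pessimistic case, since it gives the opt-out email no effect on uncalled patients, and nothing in the document suggests that calls would be missed.

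**The case for a change.** The strongest case for a change is that sections 3.1, 3.4.1, 3.4.4 and 4 speak of framing at first contact, whereas the call comes later and in one arm only. A reader of those sections alone could take a positive result as evidence about wording. A call log has to be started prospectively, and without one a partly delivered approach looks like a weak one. Section 5.6.2 also names lower trial cost as a potential benefit, and the calls use staff time.

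Some of this stands. The result should not be attributed to email text alone, and a count of calls and opt-outs by arm would help readers see what was delivered.

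The rest does not require a change. A log describes events after randomization, so it cannot separate wording from call and would not alter the primary result. Staff must in any case know who opted out in order not to call them. Cost is neither an objective in section 2 nor an outcome in section 3.4.4. Recruitment logistics may also be set out in the main trial's own protocol, which is not among the documents; section 3.3 points to it for eligibility ("Please refer to the separate protocol for inclusion and exclusion criteria for the main GAME PAD study"). A fixed date for counting enrollment would be a different definition of the outcome, since sections 3.1 and 3.4.3 count patients who ultimately enroll or consent.

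**Conclusion.** The concern describes the text correctly but calls for no change. The arms, test and intention-to-treat grouping give a valid estimate of the effect of an opt-out approach consisting of email plus announced call, which is what section 2 asks for. The remaining gap is one of description that analysts can fill when reporting: present the result as the effect of that approach and say whether opt-in patients received outbound calls. Calls and opt-outs by arm, where available, are useful description of delivery.

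The figures of 4.0 to 4.5 patients assigned per additional enrollee, and of a 25-point difference shrinking to 22.5 or 18.8, rest on the precedent rates and the assumptions shown. The 16% vs 38% contrast compared separate cohorts rather than randomized groups. None of these figures bears on the validity of the primary comparison. The conclusion would differ only if the substudy claimed an effect of email wording by itself, and its objectives do not.
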